As part of discharge criteria, the study team should assess for further monitoring of subjects who may be experiencing toxicity of Grade 3 and above (either related or unrelated to CYNK-001) at the time of discharge and consult with the treating physician. The decision to discharge a subject should be in consultation with the treating physician and clinical site study team. Physicians should follow best clinical practice to determine appropriate timing of hospital discharge.

[figure not shown]
Upon discharge, plans should be made for appropriately delegated staff to have telephone contact with subjects every day between hospital discharge through at least Day 15 visit for safety/AE monitoring. The discharge plan should include follow-up visit schedule as well as planned telehealth visit schedule.

Upon discharge, subjects will be provided with a thermometer, pulse oximeter, and blood pressure monitor for at home collection of temperature, oxygen saturation, and blood pressure with written instructions on their use as well as expectations for self-monitoring. These daily measurements will be reported via telephone to the clinical staff during each daily telehealth visit. During these daily telehealth visits, subjects are to report any new symptoms or worsening of symptoms associated with previously identified adverse events and will also provide the study team with daily vital sign measurements. Any vital signs outside of normal range will be escalated to the clinical site study team and evaluated for appropriate management.

The subject will be asked during each call to report any new or worsening symptoms that could be consistent with adverse events since the previous visit or telephone call. The investigator (or appropriately delegated study staff) will determine if medical attention or an unscheduled clinic visit is required. Each telephone call should be carefully documented with date and time of the call in the source documents and reported as appropriate.

Consultation between the Medical Monitor and appropriately delegated site staff should occur every other day after hospital discharge up to Day 15 visit for ongoing review of the subject's clinical

status. This communication may occur via telephone contact or written message (i.e. email) and should be documented accordingly.

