13.2 Efficacy Endpoints

The study includes the following efficacy endpoints:

- 1) Clinical status by OSCI at Day 28.
- 2) Clinical improvement by OSCI by Day 15.
- 3) Rate of clinical improvement by OSCI at Day 28. The rate is defined as the proportion of subjects who achieved clinical improvement by OSCI on or prior to Day 28.
- 4) Time to clinical improvement as measured by OSCI.
- 5) Time to clinical improvement by NEWS2. Time to clinical improvement by NEWS2 is defined as the time from the date of randomization (date of first dose of CYNK-001 for Phase 1) to the first date of clinical improvement by NEWS2. Clinical improvement by NEWS2 is defined as a 25% decrease compared to baseline in the NEWS2 Score. Subjects without clinical improvement by NEWS2 on or before Day 28 will be censored at Day 28.

- 6) Rate of clinical improvement by NEWS2 at Day 28. The rate is defined as the proportion of subjects who achieved clinical symptom improvement by NEWS2 Score on or prior to Day 28.
- 7) Rate of clearance of SARS-CoV-2 from mucosal specimens at Day 28. Rate is defined as the proportion of subjects with clearance of SARS-CoV-2 by rRT-PCR by two negative results at least 24 hours apart. Specimens included are nasopharyngeal swab and optional oropharyngeal swab.
- 8) Time to clearance of SARS-CoV-2 from mucosal specimens at Day 28. Clearance is defined as the time from the date of randomization to clearance of SARS-CoV-2 by rRT-PCR by two negative results at least 24 hours apart. Specimens included are nasopharyngeal swab and optional oropharyngeal swab.
- 9) Time to pulmonary clearance at Day 28. Clearance is defined as the time from randomization to the date of pulmonary clearance. This is defined as disappearance of virus from LRT specimen where it has previously been found (induced sputum and endotracheal aspirate if available).
- 10) Rate of pulmonary clearance at Day 28. Rate is defined as the proportion of subjects who had disappearance of virus from LRT specimens where it has previously been found.
- 11) Duration of hospitalization from date of hospitalization to date of medical discharge.
- 12) For subjects requiring supplemental oxygen, the days with supplemental oxygen-free up to Day 28.
- 13) Proportion of subjects who need invasive or non-invasive ventilation up to Day 28.
- 14) SOFA score for subjects admitted to the ICU from ICU admission to ICU discharge, up to Day 28.

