- Duration of hospitalization (from time from hospitalization to medical discharge up to Day 28)

The Kaplan-Meier method will be used for estimating the survival curves, the median survival time and its two-sided 95% confidence interval will be estimated. [REDACTED]

[REDACTED]

Mortality rate will be provided and be compared using Fisher's Exact Test.

For the endpoint of proportion of subjects who achieved clinical symptom improvement by NEWS2 Score by Day 28, clinical improvement is defined as a 25% reduction in NEWS2 Score. The proportions

and their two-sided 95% CIs will be calculated. Fisher's exact test will be used to test the difference between groups. If the subject has no data after baseline, the subject will be considered as failure in the analysis.

1) Calculation

- a. Respiratory rate, oxygen saturation, temperature, systolic blood pressure, and heart rate will be collected on the Vital Signs and Oxygen Saturation eCRF forms.
- b. Consciousness score will be based on the Physical Exam eCRF form. If Neurological is normal, then NEWS2 Consciousness will be scored as zero. If Neurological is abnormal, then the score will be determined based on the comments. A clinical review of the comments from the abnormal neurological findings will be required.
- c. Air or Oxygen will be based on the eCRF form Prior and Concomitant Procedure and Surgeries. If a subject had Preferred Term "Oxygen Therapy" then the NEWS2 Air or Oxygen Score will be 2 for the days from the start day through the end day of the procedure.
- d. Calculation of overall NEWS2 Score for a given day will be the sum of the scores from respiratory rate, oxygen saturation, temperature, systolic blood pressure, heart rate, consciousness, and air or oxygen categories. For infusion days, data for Vital Signs and Oxygen Saturation are collected 3 separate times. For infusion days, a separate overall score will be calculated for each time the Vital Signs and Oxygen Saturation is collected, and the worst overall score will be used as the NEWS2 Score for that day.

2) Missing data handling:

- a. If a measure for vital signs and oxygen saturation is missing, corresponding NEWS2 score will be set as missing, and the overall NEWS2 score takes the form $\geq xx$. If all categories from vital signs and oxygen saturation is missing, the overall NEWS2 score will be set as missing.

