- b. If the result for Neurological in Physical Exam is missing or not assessed, then corresponding NEWS2 score will be set as 0.
- c. NEWS2 score for "Air or Oxygen" is based on the presence of oxygen therapy in the prior and concomitant procedure page, so NEWS2 will not be considered as missing.

Ordinal data endpoints, including Clinical status by OSCI and SOFA score, will be summarized descriptively with number and percentage in each treatment arm and overall. LOCF will be used to impute missing data.

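### The SAP's NEWS2 scoring rules can record an improvement that did not occur, in the one efficacy analysis the SAP keeps without condition

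*SAP*

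**What the plan says.** **Endpoint.** SAP 13.2, item 5: "Clinical improvement by NEWS2 is defined as a 25% decrease compared to baseline in the NEWS2 Score". Time runs from randomization (first dose in Phase I) "to the first date of clinical improvement by NEWS2". No confirmation on a later day is required.

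**Consciousness item (SAP 13.3).** A normal neurological exam scores 0. "If Neurological is abnormal, then the score will be determined based on the comments", after clinical review. For an absent exam: "If the result for Neurological in Physical Exam is missing or not assessed, then corresponding NEWS2 score will be set as 0".

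**Oxygen item (SAP 13.3).** For a subject whose procedure record is coded to Oxygen Therapy, the rule reads: "then the NEWS2 Air or Oxygen Score will be 2 for the days from the start day through the end day of the procedure". Because the item depends only on whether such a record exists, "so NEWS2 will not be considered as missing".

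**Vital signs (SAP 13.3).** If one is missing, the "corresponding NEWS2 score will be set as missing, and the overall NEWS2 score takes the form" ≥xx. Only when all of them are missing is the total itself missing.

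**Entry and discharge (Protocol).** Section 8.1 allows oxygen by cannula or mask at entry, and section 8.2 excludes mechanical ventilation. After discharge, the Synopsis provides devices "for at home collection of temperature, oxygen saturation, and blood pressure with written instructions on their use". Section 12.1.4 also has vital signs taken at the outpatient facility, and its list includes respiration rate.

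**What is still to be run.** SAP 15 reports early closure with 7 subjects dosed in Phase I. It retains time to NEWS2 improvement with no condition attached. The rRT-PCR clearance and SOFA analyses are kept only if there are enough data. OSCI improvement, the Phase I primary efficacy endpoint in SAP 13.1.1, is not on the list.

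**The concern.** NEWS2 rises as a patient gets sicker, so any rule that drops points after baseline moves a subject towards the event. Two of the rules can do this as a patient deteriorates. Oxygen is allowed at entry, so the baseline can carry the 2 oxygen points. Ventilation is excluded at entry, so it can occur only later. If it is coded under another term and no oxygen record is open, the oxygen item falls from 2 to 0 at the moment support is stepped up. If the neurological exam is not done, the consciousness item is set to normal. The third rule leaves it to the programmer whether a lower bound can satisfy a test for a decrease.

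Because the event is the first qualifying day, one such day is enough, and no rule reverses it if the patient is ventilated or later dies. The only sensitivity analysis, in SAP 13.4, applies the same score to the per-protocol population. SAP 7 defines that population for Phase II only, so it cannot expose the problem here.

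**Working it through.** The plan gives no computed figure for NEWS2. Its only power figure (at least 81%, for the Phase II OSCI endpoint) is not affected.

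**Inputs.** Improvement is a 25% decrease, read as a score of 0.75 × baseline or less (SAP 13.2). Points for respiration, SpO2 scale 1, oxygen and systolic pressure come from Protocol Appendix C. The consciousness points are not in the text available to this review, so 0 to 3 is an assumed range.

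**General condition.** Let B be the baseline score, w the true change and x the points the rules fail to count. The recorded score is B + w − x. It counts as improved when B + w − x ≤ 0.75B, that is, when w ≤ x − 0.25B. With no true change (w = 0) this becomes B ≤ 4x.

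**Step 1: oxygen item lost (x = 2).** A false improvement arises for any baseline up to 4 × 2 = 8. Check: at B = 8 the recorded score is 6 and the threshold is 0.75 × 8 = 6, so the criterion is met. At B = 9 the recorded score is 7 against 6.75, so it is not.

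**Step 2: consciousness item set to 0.** At the assumed maximum, x = 3, the limit is B ≤ 12. If the oxygen points are lost as well, x = 5 and the limit is B ≤ 20. At B = 6 with x = 5, w ≤ 5 − 1.5 = 3.5, so a true worsening of 3 points still counts as improved.

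**Step 3: a worked profile.** Baseline: respiration 22 (2) + SpO2 93% (2) + on oxygen (2) = 6, so improvement needs 4.5 or less. Later the subject is intubated: rate 16 (0), SpO2 97% (0), systolic 105 (1), no open Oxygen Therapy record, neurological exam not assessed. Pulse and temperature are taken as 0 at both times.

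| Scoring | Score | Decrease from 6 | Improved? |
|---|---|---|---|
| SAP rules | 1 | 83% | yes |
| Oxygen item corrected only | 3 | 50% | yes |
| Consciousness corrected only (assumed 3) | 4 | 33% | yes |
| Both, consciousness 3 | 6 | 0% | no |
| Both, consciousness 2 | 5 | 17% | no |
| Both, consciousness 1 | 4 | 33% | yes |
| Both, consciousness 0 | 3 | 50% | yes |

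Correcting either item alone does not remove the event. Even with both corrected, some ventilated profiles still meet 25%, because a ventilator can normalise rate and saturation.

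**Step 4: incomplete vital signs.** Take an unchanged subject at B = 6 whose respiration item, worth 2, is not recorded. The total is ≥4. Read as 4, the decrease is (6 − 4)/6 = 33% and the subject is improved; read as a lower bound, no decrease is shown. Under the first reading a missing respiration item worth 2 points flips baselines up to 8, and one worth 3 points flips baselines up to 12. The SAP does not choose between the readings.

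**Step 5: weight of one subject.** With 7 subjects and no censoring before Day 28, each false event moves the proportion improved by 1/7 = 14.3 percentage points. For example, 3/7 is 42.9% (exact 95% CI 9.9 to 81.6) and 4/7 is 57.1% (18.4 to 90.1).

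**The case against.** Several stronger inferences are tempting, and the documents do not support them.

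- **That NEWS2 is the main efficacy analysis.** SAP 13.1.1 names OSCI improvement by Day 15 as the Phase I primary. SAP 15 lists analyses without ranking them, and what remains is a single-arm summary with no comparison. NEWS2 is secondary in Phase II, which will not run.
- **That every intubated patient scores as improved.** The oxygen points are lost only if ventilation is coded under another term and no oxygen record is open. The documents state neither, and Protocol 12.1.7 requires oxygen needs to be documented daily from admission to discharge.
- **That sedation automatically scores as normal.** An abnormal exam goes to clinical review. Zero arises only when the exam is missing, not assessed or recorded as normal.
- **That an incomplete total is allowed to count as improvement.** The SAP does not impute 0 for a missing vital sign. It keeps a lower bound, which cannot establish a decrease. The fault is a missing rule.
- **That respiratory rate is routinely missing after discharge.** The home devices do not measure it, but Protocol 12.1.4 provides for outpatient vital signs that include it. Nothing states that telephoned readings feed the NEWS2 score. If they do not, all vital signs for that day are missing and so is the total.

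Two further points are fair. A neurological exam missing at baseline is also scored 0, which makes improvement harder to reach. SAP 4.2 allows further missing-data rules to be set at blinded review.

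These limits narrow the point without removing it. The rules on the unassessed exam and the single oxygen term are written, and can produce a false event if followed. The allowance in SAP 4.2 is permissive and does not overturn them.

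**Conclusion.** The concern holds as a risk of bias. After baseline, the SAP 13.3 rules can move time to NEWS2 improvement towards improvement, and this is the only efficacy analysis SAP 15 keeps without condition. The firmest result is for the oxygen item: where its 2 points are lost, a subject with no true change meets the criterion at any baseline up to 8. The size for the consciousness item rests on the assumed 0 to 3 range.

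A reader might conclude that the retained analysis is corrupted. That is not shown: the number of the 7 subjects who were ventilated, unassessed or incompletely measured is unknown, and a missing baseline exam works in the opposite direction. The case for changing the rules is that one affected subject carries a seventh of the result and the correction is cheap.

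**What to change.** In SAP 13.3:

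- **(a)** Give the 2 Air/Oxygen points on any day with any recorded oxygen or ventilatory support procedure, or with OSCI 4 or higher.
- **(b)** Treat a consciousness item that was not assessed as missing, or carry forward the last assessed value, in place of 0.
- **(c)** Count an incomplete ≥xx total as improvement only if the 25% fall still holds with each missing item at its baseline value.
- **(d)** Add a sensitivity analysis in which no NEWS2 improvement is counted on a day with OSCI 5 or higher.

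Item (d) is needed because (a) to (c) do not catch every case. If the last assessed or baseline consciousness score was 0, the intubated profile above still scores 3 and counts as improved. It is put forward as a sensitivity analysis because making it the main rule would redefine the endpoint.

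The cost is SAP wording and programming for 7 subjects. Protocol 11 has OSCI recorded daily, and procedures are already on the eCRF, so no new data should be needed. The downside is that some improvements will be dated later or become non-events.

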13.4 Sensitivity Analysis

The analysis for the time to clinical improvement by OSCI, and time to clinical improvement by NEWS2 will also be performed on the PP population as sensitivity analysis.

13.5 Additional Efficacy Analysis

For either phase, the Karnofsky performance status assessment will be summarized over time by the frequencies and proportions of presence and assessment status for symptom present subjects. The proportions and the 95% confidence interval of the proportions will be provided if applicable. The descriptive statistics, including mean, standard deviation, range and 95% confidence interval of body temperature will be provided. No hypothesis testing will be performed for this part of analyses.

For phase II study, the clinical status by OSCI will be summarized overall and by each attrition over time. Mann-Whitney-Wilcoxon test will be used to compare between groups at Day 28. This analysis will be based on the ITT population without missing data imputation strategy planned.

The proportion of subjects who need invasive and non-invasive ventilation support and its 95% confidence interval will be summarized over time. Organ support related days will be also summarized by mean, standard deviation, median, range and 95% confidence interval.

14. Safety Analysis

Safety analysis will be based on the safety analysis population. For Phase I, the analysis will be performed by cohort, including an overall column. For Phase II, the analysis will be performed by treatment arms.

14.1 Adverse Events

All AEs will be coded using the MedDRA dictionary Version 23.0 or higher. The severity of toxicities for AEs will be graded 1 to 5 according to the National Cancer Institute Common Terminology Criteria for Adverse Events (NCI-CTCAE) Version 5.0 whenever possible. AEs with missing severity will be presented in the summary table as missing category.

A treatment-emergent adverse event (TEAE) is defined as an AE which started on or after the first dosing date of the study drug or an existing condition being worse on or after the first dosing date of the IP.

Adverse events with unknown onset date and with end date after first dosing date will be counted in the TEAE.

A treatment-related AE is defined as an AE which is considered to be of suspected relationship to the study drug. Adverse events with missing relationship to study drug will be assessed as treatment-related.

The following summaries will be provided:

- A table for overall summary and a listing of all AEs by SOC and PT will be provided for AEs that occurred during the screening period.
- Separate summaries will be provided for the treatment period (Day 1 – Day 28) and follow-up period (Day 29 to 6 months). The following summary tables will be generated:
 - Overall summary
 - All TEAEs by SOC and PT
 - TEAEs that satisfy the DLT criteria (Phase I treatment period only)
 - TEAEs leading to discontinuation of treatment
 - TEAEs with toxicity grade ≥ 3
 - Drug-related TEAEs
 - Serious TEAE
 - TEAEs that led to death
 - Summary of CRS

If a subject experiences multiple AEs under the same PT (SOC), then the subject will be counted only once for that PT (SOC). If a subject experiences the same AE more than once with different toxicity grade, the event with the highest grade will be tabulated in “by maximum toxicity grade” tables.

14.2 Laboratory assessment

Laboratory results including chemistry and hematology, will be summarized over time. Absolute change from baseline to each study day up to 6-month follow-up, will be summarized descriptively with mean, standard deviation, median, range and 95% confidence interval by visit.

14.3 Vital signs

Vital signs and the changes from baseline will be summarized descriptively with mean, standard deviation, median, range and 95% confidence interval by infusion time point at Day 1, Day 4 and Day 7. The clinically significant status of vital signs will also be tabulated. During the infusion day, the summary of vital signs will be summarized separately by infusion time point as pre-infusion, 30 minutes post-infusion and 4-hours post infusion.

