Subjects treated in the Phase II portion of the study will be treated either in the inpatient or outpatient setting, as determined after review of data from the Phase I portion of the study and based on DMC recommendation. The level of outpatient monitoring of subjects treated in the Phase II portion will be determined based on review of Phase I data and DMC recommendation.

A de-escalation dose (Dose -1) will be initiated based on the study safety stopping rules and dose-limiting toxicities. Dose de-escalation is defined as reducing the frequency of the doses (without reducing the total number of cells given per dose) by providing doses only on Days 1 and 7 due to any potential safety concerns per DMC recommendation.

On each day of CYNK-001 infusion, subjects will be pre-medicated and post-medicated with acetaminophen 650 mg orally (PO) and diphenhydramine 25 mg (PO/IV) at least 30 minutes prior to and approximately 4 hours following the end of the CYNK-001 infusion. Meperidine may also be administered to control rigors, if clinically indicated. Subjects must be monitored for at least 4 hours after completion of each CYNK-001 infusion.

All subjects (even in control arm) should meet the inclusion/exclusion criteria.

The control arm subjects in the Phase II portion of the study will receive the best supportive care as defined by the institutional practice without CYNK-001. All subjects in both Phase I and Phase II will receive the best supportive care.

Additional testing including blood, nasopharyngeal and oropharyngeal (optional) swabs, and sputum (optional) may be collected for research purposes. In some cases, customary standard of care procedures may be conducted more frequently for the purpose of this clinical study.

Information will need to be gathered and entered in the EDC associated with the medical management of the subject.

Follow-up Period (Day 29 to 6 months):

The follow-up period is defined from Study Day 29 to 6 months. The Subjects will be followed at 3 months, and 6 months or until loss to follow-up, death, or withdrawal from study whichever occurs first.

The study will be conducted in compliance with ICH Good Clinical Practices (GCPs) and in concordance with local Health Authority regulations.

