12.1.4. Vital Signs

Vital signs will be measured, including temperature, systolic and diastolic blood pressure, respiration rate, and pulse and oxygen saturation (SpO₂), per standard institutional practice as outlined in the Table of Events.

Vital signs to be collected from medical record during hospitalization. Once subject is discharged the vital signs should be collected in the outpatient facility where the subject is seen.

Upon discharge, plans should be made for appropriately delegated study staff to have telephone contact with subjects every day between hospital discharge through at least Day 15 visit for safety/AE monitoring. Subjects will be provided with a thermometer, pulse oximeter, and blood pressure monitor for at home collection of temperature, oxygen saturation, and blood pressure with written instructions on their use as well as expectations for self-monitoring. These daily measurements will be reported via telephone to the clinical staff during each daily telehealth visit. During these daily telehealth visits, subjects are to report any new symptoms or worsening of symptoms associated with previously identified adverse events and will also provide the study team with daily vital sign measurements. Any vital signs outside of normal range will be escalated to the clinical site study team and evaluated for appropriate management. The subject will be asked during each call to report any new or worsening symptoms that could be consistent with adverse events since the previous visit or telephone call. The investigator (or appropriately delegated study staff) will determine if medical attention or an unscheduled clinic visit is required. Each telephone call should be carefully documented with date and time of the call in the source documents and reported as appropriate.

On each day of CYNK-001 infusion, vital signs to be collected pre-infusion, approximately 30 minutes after the start of infusion, and approximately 4 hours after the completion of infusion.

On non-infusion days where multiple vital signs are collected throughout the day, vital signs should be captured in the EDC once per day and the worst vitals should be recorded.

Note: Subjects must be monitored for at least 4 hours after completion of each CYNK-001 infusion.

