All subjects will be monitored for AEs during the study. **Infusion related reactions (IRRs) will be documented for the first 72 hours of CYNK-001 infusion at every dose.** Assessments may include monitoring of any or all of the following parameters: the subject's clinical symptoms, laboratory, pathological, radiological or surgical findings, physical examination findings, or findings from other tests and/or procedures.

All AEs that occur after any subject has been enrolled, before treatment, during treatment, or within 28 days following the first CYNK-001 infusion (to Study Day 28), whether or not they are related to the study, must be recorded on forms provided by Celularity.

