14.5. Safety Analysis

Safety analysis will be based on the Safety Population. Descriptive statistics will be provided for AEs, vital sign measurements, physical examination findings, clinical laboratory test results, infusion site assessments, and concomitant medications and procedures.

AEs observed will be classified using the MedDRA classification system (MedDRA version 23.0). The severity of the toxicities will be graded according to the NCI CTCAE, version 5.0 whenever possible. Adverse events will be summarized by MedDRA system organ class and preferred terms, and separate tabulations also will be produced for related adverse events, SAEs, discontinuations due to adverse events, and events of at least Grade 3 severity. A summary of the number and severity of CRS AEs will also be produced. AEs will be summarized by study period for those events that occur during the study periods.

Vital signs data and laboratory data will be tabulated for changes over time.

Laboratory parameters will be summarized for changes across study using descriptive statistics including shifts relative to CTCAE criteria for laboratory abnormalities. Laboratory measures will also be compared with their corresponding normal ranges, and the incidence of abnormally high and abnormally low laboratory values will be summarized.

Graphical displays may be provided where useful in the interpretation of results.

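### SAP 14.3 ties the descriptive vital-sign summary to infusion time points on Days 1, 4 and 7, which is narrower than protocol 14.5, and it mislabels the 30-minute reading

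*SAP*

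**What the plan says.** SAP 14.3 summarises vital signs and change from baseline "by infusion time point at Day 1, Day 4 and Day 7", with separate results for "pre-infusion, 30 minutes post-infusion and 4-hours post infusion". One further sentence in 14.3 carries no day restriction: "The clinically significant status of vital signs will also be tabulated".

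The protocol is wider in three places:

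- **Planned analysis (14.5):** "Vital signs data and laboratory data will be tabulated for changes over time".
- **Endpoint (5.4, Table 2):** changes in vital signs are a named component of the Phase I primary safety endpoint, and of Phase II safety to Month 6.
- **Collection (12.1.4):** on non-infusion days with several readings, "vital signs should be captured in the EDC once per day and the worst vitals should be recorded".

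The protocol also sets its own risk windows. Section 12.3.1.1 says infusion-related reactions "will be documented for the first 72 hours of CYNK-001 infusion at every dose". Section 6.3 counts CRS of Grade 3 or above as a dose-limiting toxicity up to Study Day 28. On infusion days, protocol 12.1.4 takes the middle reading "approximately 30 minutes after the start of infusion".

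**The concern.** The table that describes measured vital signs follows the infusion schedule, while the protocol's safety windows run on after it. Fever, hypotension and hypoxia are the elements of CRS grading in protocol Table 7. A reaction that develops on the days between doses, or after Day 7, would not appear in this table even where the values were recorded.

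The restriction looks specific to vital signs. SAP 14.2 summarises laboratory change at each study day up to the 6-month follow-up, and SAP 14.5 summarises inflammation markers over time. SAP section 15, which lists changes from the protocol, does not mention the narrowing.

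Two smaller defects sit in the same paragraph of SAP 14.3. The middle time point is described differently from the protocol. And a table built on infusion time points has no place for Phase II controls, who receive no infusion, although SAP section 14 promises Phase II safety results by treatment arm.

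**Working it through.** The plan gives no figure to reproduce. The check compares passages and counts days.

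**1. Coverage of the 14.3 table.** There are 3 infusion days with 3 readings each, so at most 3 × 3 = 9 readings per subject. On schedule the last is about 4 hours after the Day 7 infusion. The treatment period ends on Day 28, so 28 − 8 + 1 = 21 study days lie after the table stops.

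**2. How many of those 21 days would have data.** The vital-sign rows of the Table of Events are not visible, so this is a range under stated assumptions.

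| Assumption about the subject | Days after Day 7 with vital signs |
|---|---|
| In hospital through Day 28, recorded daily | 21 |
| Discharged on Day 8, daily readings through Day 15 all entered, plus Days 21 and 28 | 8 + 2 = 10 |
| Discharged on Day 8, only the Day 15, 21 and 28 visits entered | 3 (plus any discharge-visit reading) |

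The protocol requires daily calls through at least Day 15 after discharge. It does not say that home readings given by telephone are entered in the EDC.

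**3. The 72-hour window.** On schedule, the pre-infusion readings on Days 4 and 7 fall about 72 hours after the previous dose, so the table has a value near the end of the first two windows. Days 2, 3, 5 and 6 are absent. After the third dose nothing later than about 4 hours is tabulated. SAP 14.1 lists no infusion-reaction table and no 72-hour summary.

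**4. Consecutive-day fever.** Protocol 12.6.2 names fever of at least 38°C for at least 3 consecutive days as a marker of risk for severe CRS. No two of Days 1, 4 and 7 are adjacent, so the 14.3 table cannot show it.

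**5. The other outputs that touch these signs.**

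- SAP 14.1: treatment-period tables of all events, Grade 3 or above, DLT events and CRS. Protocol 12.3.1.7 has CRS symptoms captured and graded separately. These depend on what investigators report.
- SAP 14.3: the clinical-significance tabulation, with no days stated.
- SAP 13.5: body-temperature mean, SD, range and confidence interval. It has no count at or above 38°C, and no blood pressure or SpO2.
- SAP 13.3: a NEWS2 score for each day, analysed as a 25% reduction. It uses these vital signs but measures improvement.
- SAP 14.7: subject listings.
- SAP section 15: vital-sign and oxygen-saturation summaries with shifts from baseline, naming neither days nor categories.

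**6. The label.** The SAP reading is after infusion; the protocol reading is after its start. The two clock times differ by the length of the infusion. A recommended rate of about 240 mL per hour is given, but the infused volume is not in the available text, so the gap cannot be computed.

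**The case against.** The strongest reply is that fever, hypotension and desaturation are covered elsewhere. A reader might infer from SAP 14.3 that they have no planned analysis after infusion days. The documents do not support that: the event, DLT and CRS tables run to Day 28, the clinical-significance tabulation has no day limit, and temperature, NEWS2 and listings are all planned. SAP 4.7 also selects safety observations for every study day in the treatment period, which presupposes data beyond infusion days. This part of the reply stands and limits the point to the descriptive summary.

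Three other tempting readings also fail.

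- **That 25 of 28 treatment days of data are lost.** This assumes daily recorded vital signs for everyone. Subjects may leave hospital on Day 8, and later recording is uncertain.
- **That only 4 of each 72 hours is seen.** This overlooks the pre-infusion readings on Days 4 and 7.
- **That required medication makes the tabulated readings look normal.** Pre- and post-medication is given "at least 30 minutes prior to and approximately 4 hours following the end of the CYNK-001 infusion". Acetaminophen bears on temperature, and blunting there is an inference the documents do not state. The second dose falls around the 4-hour reading and need not precede it. Nothing supports masking of blood pressure or SpO2.

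It is also fair to say that section 15 does not simply point back to 14.3. It names shifts and oxygen saturation, which 14.3 does not. So which days the surviving summaries cover is unstated rather than restricted.

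Finally, the trial closed with 7 subjects dosed in Phase I. Listings can show every recorded value for 7 people, and the control-arm problem does not arise unless Phase II is analysed. That lowers the weight but does not align SAP 14.3 with the protocol.

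**Conclusion.** The point holds in limited form. SAP 14.3 states a rule, not a mere omission, that leaves vital signs between and after infusion days out of the descriptive summary. That is narrower than protocol 14.5 and than an endpoint defined by changes in vital signs. On schedule 21 treatment-period days lie beyond the table, of which somewhere between 3 and 21 would carry data per subject under the assumptions shown. Delayed changes would be seen mainly through reported events, an undated tabulation, a temperature summary and listings. These are real analyses, but the event tables depend on investigator reporting, listings are not summaries, and none is a by-day account of blood pressure or SpO2.

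The label discrepancy is a plain contradiction between SAP and protocol. The missing Phase II control time points follow directly from the design of the table. Practical weight is low with 7 Phase I subjects dosed, but the correction is cheap and uses values already recorded.

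**What to change.** In SAP 14.3, and for the section 15 summaries of vital signs and oxygen saturation:

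1. Add change from baseline by study day or visit over the treatment period, for temperature, blood pressure and SpO2 at least. Use the recorded daily worst value where there is one, and show the number of subjects with data at each day.
2. Include the days within 72 hours of each dose.
3. State which reading represents an infusion day. SAP 4.7 would take the latest, whereas the NEWS2 rule in SAP 13.3 takes the worst score of the three collection times. The worst reading is consistent with the non-infusion-day recording rule.
4. Add a count of subjects with temperature at or above 38°C, the threshold already in protocol 12.6.2.
5. If Phase II is analysed, use the same by-day table for both arms.
6. Change the label of the middle reading to 30 minutes after the start of infusion.

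Counts of subjects crossing the NEWS2 score-3 cut-offs for systolic pressure and SpO2 are optional. They would not reproduce CRS grade, which protocol Table 7 bases on vasopressor need and mode of oxygen delivery.

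The cost is SAP wording and one or two tables, with no change to data collection or clinical management. With 7 subjects the tables will be sparse and should be read alongside the listings.
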